## Abstract

The remodeling of the alveolar bone following tooth extraction results in significant bone loss at the extraction site. An excessive bone loss hampers the implementation of treatment plans, prediction of esthetic outcomes, and patient satisfaction. Placing bone substitute materials in an extraction socket may reduce the alveolar bone resorption. However, postoperative infection and inflammation are common side effects following bone graft surgeries. Finding a less invasive approach to preserve the alveolar ridge would be amenable to dental clinic. An animal study reported that bone density significantly increased in the extraction site with transcortical mini-screw placements, exhibiting markedly less atrophied alveolar ridge. In addition, the side effects from a mini-screw placement are minimal and no antibiotics are required. Therefore, we propose the placement of a transcortical mini-screw at the buccal plate of an extraction socket as a minimally invasive approach to preserve the alveolar ridge. The objective of this study is to determine the effects of transcortical mini-screws placed at the buccal plates of the extraction sockets in humans. We hypothesize that placement of a transcortical mini-screw at the buccal plate will significantly reduce bone loss at the site. To test this hypothesis, we are performing a prospective split-mouth design study. We are recruiting patients who need extraction of two maxillary premolars for orthodontic treatments. Cone beam computed tomography (CBCT) is exposed after the extraction of two premolars and before a transcortical mini-screw placement ( $T_0$ ). One 8-mm length mini-screw is placed at the buccal plate of the extraction socket on one side. The contralateral extraction socket is untreated. The mini-screw is removed at 6 months and the follow-up CBCT is obtained ( $T_6$ ). We will compare changes in the alveolar bone width at both extraction sides using the CBCTs. We predict that the placement of a transcortical mini-screw at the buccal plate of the extraction socket significantly reduces bone loss at the extraction site. Results of this study will offer a useful measure to sustain an edentulous alveolar ridge for a lengthy period without losing bone proper.

[figure not shown]
## Research Plan

### SIGNIFICANCE AND INNOVATION

**Bone loss following tooth extraction is inevitable but current available procedures for preserving bone after tooth extraction are not satisfactory.** Teeth develop from tooth buds in the jaw bone, known as alveolar bone. The alveolar bone undergoes constant remodeling process throughout the life of teeth. When teeth are extracted, the surrounding alveolar bone remodels and undergoes atrophy, resulting in reduced alveolar ridge in width and height, most of which takes place in the first 3 months after tooth extraction (Fig 1). Within six to eight weeks, the total ridge thickness was reduced by 15% of the original value in average. The ridge width was reduced from 12 mm at baseline to 6 mm at 12 months. Such bone reduction hampers the success of treatments such as implant placements, esthetics for ideal fixed dental restorations, and orthodontic teeth treatment through the edentulous space. To modify bone remodeling after tooth extraction, various surgical ridge preservation procedures were proposed using bone substitute materials in conjunction with barrier membranes.

However, extractions often occur without planning. Bone graft/ridge preservation surgeries may not be feasible at the time of extraction due to a lack of finance, insufficient time, and/or a lack of treatment plan. In addition, inflammation and postoperative swellings commonly occur after ridge preservation surgeries, thus, antibiotics are prescribed after the surgeries. A minimally invasive and cost-effective approach to preserve the alveolar ridge following tooth extraction is desirable.

**We propose a transcortical mini-screw insertion in order to preserve edentulous ridge as a minimally invasive (no antibiotics prescription requiring) and cost-effective (\$180) approach.** Transcortical mini-screws are widely used in orthodontic treatments for temporary anchorage purposes. Transcortical orthodontic mini-screws are not fully integrated but maintain contact with alveolar bone ranged from 10% to 58% of surface, which makes it easy to be removed after orthodontic treatments. In addition, the side effects of transcortical mini-screws such as per-implant inflammation are extremely low. One of the premises of our proposal is an animal study showing that a placement of transcortical mini-screw at the buccal plate of an extraction socket significantly increased bone density in the extraction site, which resulted in markedly less atrophy of alveolar ridge. Furthermore, a case report indicates that insertion of transcortical mini-screws in the alveolar plate may result in increased bone density in the region. However, clinical studies determining the effects of a transcortical mini-screw placement on ridge preservation is lacking. The objective of our study is to investigate effects of a transcortical mini-screw placement on alveolar ridge preservation after tooth extraction. Successful outcomes will suggest the potential novel clinical application of the mini-screw for ridge preservation after tooth extraction, which can greatly enhance dental practice.

**Figure 1. Schematic of alveolar bone changes following tooth extraction.** A. Bone loss following tooth extraction is problematic for functional and esthetic restoration. B. In this study, we predict that mini-screw placement in the buccal plate of extraction socket will reduce the bone loss (lower), which should enhance prognosis of the restoration.

## **THE OBJECTIVE**

The objective of our study is to investigate effects of a transcortical mini-screw placement on alveolar ridge preservation after tooth extraction.

## **SPECIFIC AIMS**

Specific Aim 1: To evaluate the clinical outcomes between the treated sites with a transcortical screw (the experimental group) and the non-treated sites (the control group)

*Null Hypothesis:* There will be no differences in clinical parameters between the two groups.

*Approach:* The investigators will conduct a prospective split-mouth design clinical study. The investigators will compare the clinical changes in the vertical ridge height and the horizontal ridge width at 3 months and 6 months from baseline (tooth extraction).

Specific Aim 2: To evaluate the radiographic outcome between the experimental and the control group

*Null Hypothesis:* There will be no difference in alveolar bone height and width between the two groups.

*Approach:* The study will measure the alveolar bone heights and widths using cone beam computed tomographies (CBCTs) at baseline and 6 months.

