### 3. Research Procedures (Figure 2)

1) Obtaining signatures on the consent form at screening visit.

The PI and the POC will follow the protocol in the approved IRB application while we are obtaining signatures from the potential subject. The information will be given to the potential subject in the separate room. The potential subject will be encouraged to ask the PI and the POC any questions regarding this protocol. (Approximately 40 to 60 minutes)

2) Placement of a mini-screw at the buccal plate of the extraction socket in one side (left or right) one week after the atraumatic extraction of maxillary premolars

- Limited volume CBCT with high resolution will be exposed before the mini-screw placement; this is standard of care.
- Clinical photographs and intraoral images will be obtained for both sites.
- One mini-screw (8 mm length) will be placed at the buccal plate of one extraction site. After bone sounding, a mini screw will be placed at the position 3 mm from the alveolar crest. The other extraction site will be untreated. (Approximately 30 minutes)
  - The PI and the POC will monitor subjects closely.
  - Local anesthesia with lidocaine will be administered to minimize patients' discomfort.
  - Postoperative instruction will be given to subjects.

3) 3 months follow-up (30 minutes); Clinical photographs and intraoral images will be obtained for both sites.

[figure not shown]
4) 6 months follow-up (40 minutes)

- The mini-screws will be removed.
- Clinical photographs and intraoral images will be obtained for both sites.
- Limited volume CBCT with high resolution will be exposed; this is a study procedure.

**Figure 2.** Intraoperative photographs from one of subjects. (a) Mini-screw (arrow) placed 1 week after extraction. (b) 3-month follow up. (c) 6-month follow up after removal of screw.

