**4. Radiographic Measurements:** CBCT will be exposed after teeth extraction and before the mini-screw placement ( $T_0$ ). One mini-screw will be placed at the buccal plate of the extraction socket one week following the extraction of maxillary premolars in one side. The other extraction socket site will be untreated. At 6 months, the follow-up CBCT will be exposed for the maxilla after removal of the mini-screws. A blinded evaluator will measure the width of alveolar ridge on the CBCTs made at  $T_0$  and  $T_6$ . Changes in the width of alveolar ridge were measured from the outer wall at  $T_0$  to the outer wall at  $T_6$ . A positive value indicates bone loss. In the sagittal section, three levels will be determined by measuring from the crest to the apex and dividing the socket length into thirds. The measurements will be performed in coronal and axial sections (Figs 3a and 3b).

**Figure 3.** Measurements of bone loss after tooth extraction on CBCTs. (a-b) Examples of coronal (a) or axial (b) measurements. Changes of bone level from  $T_0$  to  $T_6$  was measured. Superimposition of two CBCT images ( $T_6$ , blue;  $T_0$ , grey) was performed using Invivo 6.0 software. Right side images present magnification of insets in left panels. (c-d) Changes in the width of alveolar ridge (mean  $\pm$  SD) in the experimental (exp) and the control (con) side at the crestal (C), middle (M), and apex (A) level in coronal or axial sections.

**5. Interim data and statistical analysis:** No inflammation and infection related to the mini-screw placements were observed in all 6 subjects. Miniscrews were removed at 6 months from 3 subjects and at 8 months from 3 subjects (the mean of 7-month) in keeping with planned dental treatments. Overall, the experimental side with the miniscrew placement showed less bone loss than the control side at the crestal, middle, and apex level in both coronal and axial measurements (Figs 3c and 3d). Upon completion of the study, a paired t-test will be performed to compare the changes in the width of alveolar ridge from the two sides. We will also measure mineral density distribution at the extraction sites from the two sides using CBCTs.

**6. Expected outcomes:** We predict that the experimental side with mini-screw placements will exhibit a significantly less bone loss than the control side. Bone density in the experimental side will be significantly greater than the control side.

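### Must the plan be changed because CBCT bone height and the clinical ridge dimensions appear in the aims without a defined reading or test?

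*Combined protocol and SAP*

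**What the plan says.** The Specific Aims name more outcomes than the Approach develops.

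- **Aim 2 (radiographic).** "The study will measure the alveolar bone heights and widths using cone beam computed tomographies (CBCTs) at baseline and 6 months". Its null hypothesis covers both dimensions: "There will be no difference in alveolar bone height and width between the two groups".
- **Aim 1 (clinical).** "The investigators will compare the clinical changes in the vertical ridge height and the horizontal ridge width at 3 months and 6 months", with tooth extraction as the baseline.
- **Abstract.** Only one dimension is mentioned: "We will compare changes in the alveolar bone width at both extraction sides using the CBCTs".
- **Approach, Section 1.** The primary outcome is the difference in mean ridge width between sides. The revised target of 14 subjects is stated for a 0.5 mm width difference.
- **Approach, Section 3.** Images of both sites are taken at screw placement, one week after extraction, and again at 3 and 6 months. The 3-month entry reads: "3 months follow-up (30 minutes); Clinical photographs and intraoral images will be obtained for both sites".
- **Approach, Section 4.** "A blinded evaluator will measure the width of alveolar ridge on the CBCTs made at" T0 and T6. The crest and apex enter only to set the measuring levels: "three levels will be determined by measuring from the crest to the apex and dividing the socket length into thirds".
- **Approach, Section 5.** The paired t-test is specified for width change. Mineral density will also be measured, with no test named.

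**The concern.** Read against each other, the aims and the methods do not match. Aim 2's null hypothesis includes bone height, yet no height landmark, reader or test is given. Aim 1 is wholly about clinical dimensions, yet the visits list only photographs and intraoral images, with no scale, reference point or assessor. Aim 1 also counts from extraction, while the first listed images come a week later.

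Two things could be at stake. The trial might finish with half of Aim 2 and all of Aim 1 unanswered, although the Significance and Innovation section describes ridge loss in both width and height. And because width data from six subjects have already been analysed, a height landmark chosen late could be chosen to suit the result.

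**Working it through.** **Step 1: count what is named and what is defined.**

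| Comparison | Named in | Data source scheduled? | Reading and test defined? |
|---|---|---|---|
| CBCT width, baseline to 6 months | Aim 2 | Yes, T0 and T6 scans | Yes (Sections 4 and 5) |
| CBCT height, baseline to 6 months | Aim 2 | Yes, same scans | No |
| Clinical height, 3 months | Aim 1 | Images of both sites | No |
| Clinical width, 3 months | Aim 1 | Images of both sites | No |
| Clinical height, 6 months | Aim 1 | Images of both sites | No |
| Clinical width, 6 months | Aim 1 | Images of both sites | No |

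Clinical: 2 dimensions × 2 times = 4. CBCT: 2 dimensions. Total 6, of which 1 is fully defined and 5 are not. All six have a scheduled source, although the text does not say whether the clinical images carry dimensions.

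**Step 2: does the gap reach the primary result?** No. The blinded reader, the three levels and the paired test all concern width. The sample size is also stated for width. The figure of 14 cannot be reproduced because the interim SD is not given. Working backwards, a two-sided paired t-test at α = 0.05 with 14 pairs has 80% power at a standardised difference of 0.810, so the implied SD of the paired difference is 0.5 / 0.810 = 0.62 mm. None of this involves height or the clinical outcomes.

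**Step 3: can height still be read?** Yes. Section 4 already has the crest and apex located in order to divide the socket into thirds, and the Figure 3 caption describes superimposing T0 and T6. One landmark, two sides and two times give 14 × 2 × 2 = 56 readings if the 14 include the six completed subjects, or 20 × 2 × 2 = 80 if they do not. No extra visit or scan is needed.

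**Step 4: does the baseline mismatch bias the comparison?** Both sides of a subject share the same dates, and the screw cannot act before it is placed. Starting from the placement visit leaves a within-subject comparison of sides intact.

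**Step 5: does the mixed removal time matter here?** Three of the completed subjects had removal at 6 months and three at 8: (3 × 6 + 3 × 8) / 6 = 7.0 months, which matches Section 5. The plan discloses this. It applies equally to width, and both sides of a subject share the same follow-up.

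**Step 6: would formal tests for the other five be a gain?** If five independent tests were each run at 0.05, the chance of at least one false positive would be 1 − 0.95⁵ = 0.226, about 23% (independence is an assumption). Precision would be modest: with 14 pairs, the 95% half-width is 2.160 / √14 = 0.577 SDs of the paired difference. The documents give no height SD; an assumed 0.5 to 1.0 mm gives ±0.29 to ±0.58 mm. Estimates with intervals, labelled secondary, are what such data support, and a formal test for each would add little.

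**The case for a change.** The strongest case for a change is that both null hypotheses are stated as formal aims, so calling them secondary does not excuse leaving them without a method. Extending the paired t-test to height supplies a test but no landmark. The trial is ongoing, six subjects' width results have been seen, and no height result has been reported, so fixing the landmark now would be cheap and would close off selective choice later. If the images carry no scale, a quantitative claim under Aim 1 would have no support.

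Much of this stands as description. This document does not define the height reading or the clinical readings, and a landmark fixed before any height is read is better than one fixed after.

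It falls short of a required change for three reasons. First, Aim 2 already commits to the modality, sites and times for height, so what is missing is working detail. Second, there is no one right repair. A buccal apex-to-crest distance would narrow Aim 2, which does not restrict height to the buccal side; dropping height or reporting it descriptively would be equally defensible. Third, the Aim 1 remedy depends on what the images contain, which the documents do not say. The argument about selective choice concerns a non-primary outcome and leaves the width comparison alone.

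**Conclusion.** The mismatch is real but needs no change to the plan. Five of the six comparisons named in the aims lack a written reading and test. All five are non-primary, and the one that carries the sample size and the main conclusion is defined and unaffected. An analyst would sensibly fix a height landmark on the T0 and T6 scans, use the same blinded reader and within-subject comparison, and report clinical dimensions only as far as the images allow. The unnamed density test and the extraction-versus-placement baseline are gaps of the same kind.

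This rests on three assumptions: that the scans show crest and apex at both sites, as the division into thirds requires; that height, density and the clinical dimensions are reported as secondary to width; and that any quantitative claim under Aim 1 is made only if the images can be measured. The effect on the primary width comparison is nil. The documents give no SD for height, so the consequence for height cannot be put in millimetres beyond the assumed range shown above.

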## **APPROACH**

This is an on-going prospective clinical study under a protocol approved by the IRB (HP-00076020). Six subjects completed the study protocol. Interim data analysis was performed from these six subjects.

1. Sample size determination: The original sample size was determined to provide 80% power to recognize a significant difference of 1 mm between the two sides with a 95% confidence interval ( $\alpha=0.05$ ) and standard deviation of 1.0 mm, considering the difference in the mean width of the edentulous alveolar ridge as the primary outcome variable. Based on the power analysis reperformed by following the formula described by Faul et al using the interim data from the 6 subjects, 14 subjects will provide 80% power to recognize a significant difference of 0.5 mm in the width of the alveolar ridge between the two sides.

2. The Study Population: Patients with the following conditions are included: a) age  $\geq 18$  years, and b) two maxillary premolars (one from the left side and the other from the right side) required to be extracted in accordance with recommended dental treatment plans. Exclusion criteria are as follows: a) hyper-/hypothyroid dysfunctions, b) diabetes mellitus, c) subjects with a history of a chronic use of corticosteroid ( $> 6$  months), d) subjects with a history of taking oral/IV bisphosphonates within the past 2 years, e) smokers, and f) other systemic conditions influencing bone integrity.

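### Does re-sizing the study to 14 from six subjects' by-side data require a different final test from the planned paired t-test?

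*Combined protocol and SAP*

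**What the plan says.** The Approach section opens with "This is an on-going prospective clinical study under a protocol approved by the IRB", and adds that six subjects had completed it and that "Interim data analysis was performed from these six subjects". The Abstract, in the present tense, says "We are recruiting patients who need extraction of two maxillary premolars for orthodontic treatments".

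Item 1 (Sample size determination) gives two calculations. The first: "The original sample size was determined to provide 80% power to recognize a significant difference of 1 mm between the two sides", with alpha 0.05 and an SD of 1.0 mm, "considering the difference in the mean width of the edentulous alveolar ridge as the primary outcome variable". The resulting number of subjects is not stated. The second: "using the interim data from the 6 subjects, 14 subjects will provide 80% power to recognize a significant difference of 0.5 mm". The SD behind it is not in the text.

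Item 5 (Interim data and statistical analysis) shows that the look was comparative: "Overall, the experimental side with the miniscrew placement showed less bone loss than the control side", and it says this held for all three levels and both planes. It reports no test, p-value or claim of success from the six. It plans a paired t-test of the width changes once the study is complete and mentions no adjustment.

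**The concern.** An ordinary t-test holds its level when the sample size is fixed or is chosen without regard to the data being tested. Here the number was revised after the two sides had been compared in six subjects, and the detectable difference moved from 1 mm to 0.5 mm. If those six are pooled with eight more, the rule that turned interim data into N becomes part of the design, and the nominal 0.05 is no longer assured. The study is small and sized at about 80% power, so a p-value near 0.05 is a realistic result and could be challenged on the design alone. The plan does not say whether the six are counted, what set N, or why 0.5 mm was chosen.

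**Working it through.** **Inputs from item 1.** Alpha 0.05 (taken as two-sided, since sidedness is not stated); power 80%; 1 mm with SD 1.0 mm at first; 0.5 mm and N = 14 after the look. Assumed: the interim SD and the re-sizing rule.

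**Sample sizes.** For a paired t-test, power = P(T > t_{0.975, N−1}), where T is noncentral t with N−1 degrees of freedom and noncentrality dz·√N, and dz = difference / SD of within-subject differences.

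- Plan's N = 14: 80% power needs dz = 0.810, so SD = 0.5/0.810 = 0.617 mm. N = 13 would need dz = 0.847, so SD = 0.5/0.847 = 0.59 mm. An SD of differences of about 0.59 to 0.617 mm therefore gives 14. That is a plausible interim value, and nothing shows the figure to be wrong.
- Original inputs, SD 1.0 mm read as that of differences: dz = 1.0. N = 9 gives 74.8% and N = 10 gives 80.3%, so N = 10.
- 0.5 mm with SD 1.0 mm of differences: dz = 0.5. N = 33 gives 79.5% and N = 34 gives 80.8%, so N = 34.

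**Type I error if the six are pooled.** Under no difference, the first six values set N within a minimum and maximum, and all N are then tested at two-sided 0.05 (400,000 runs per cell, Monte Carlo error about 0.04 points).

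| What set N | Min N | Max 14 | Max 20 | Max 34 |
|---|---|---|---|---|
| Interim SD only, true SD 0.62 mm | 10 | 5.5% | 5.7% | 5.9% |
| Interim SD only, true SD 1.0 mm | 10 | 5.3% | 5.6% | 5.9% |
| Observed effect and SD | 10 | 5.7% | 6.3% | 6.9% |
| Interim SD only, true SD 0.62 mm | 6 | 6.7% | 7.0% | 7.2% |
| Interim SD only, true SD 1.0 mm | 6 | 5.8% | 6.0% | 6.4% |
| Observed effect and SD | 6 | 7.1% | 7.7% | 8.3% |

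Reference cases: N fixed at 14 gives 5.0%. Raising N from 10 to 14 only when the interim |t| exceeds 1 gives 4.2%, so even the direction depends on the rule. If the 14 are all new subjects, this source adds nothing.

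The wording of item 1 sets 0.5 mm in the same grammatical place as the original 1 mm. That fits a target difference combined with an interim SD better than an observed effect, without excluding the latter.

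**Price of the alternatives**, at dz = 0.81:

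- Pooled paired t-test on 14: 80% power.
- Inverse-normal combination of the six and the eight new subjects: 78% with equal weights; 77% with squared weights 6/10 and 4/10 from an original N of 10.
- Eight new subjects alone: 51% (54% if the SD is 0.59 mm).

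**The case for a change.** The best argument for a change is that the excess cannot be bounded from the documents, so the sponsor cannot show that 0.05 holds, whereas a two-stage combination test would hold it for two to three points of power and no extra subjects. The present-tense recruiting and the single continuing protocol also make it more likely than not that the six are counted.

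Part of this stands. The two missing facts are worth stating when results are reported, and a two-stage analysis beside the main one would be a reasonable sensitivity check.

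It falls short of requiring a new primary test for three reasons. First, the weights would now be chosen after the look, because no original N is printed to derive them from. Second, a combination test protects the level only if the single width measure it uses was not picked from the interim results. Item 5 lists three levels in two planes and item 1 does not say which is primary. Averaging all six is no neutral default, since item 8 (Potential limitation) gives the levels different clinical roles and says coronal sections show palatal loss poorly. Third, the 77% to 78% power applies the dz implied by N = 14 for an unnamed measure, and need not carry over to a new composite.

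**Conclusion.** No change to the plan follows. The facts behind the concern are correct: N was revised using by-side data from six subjects, and the final test is unadjusted. What the documents establish is missing detail, not an invalid analysis. If the six are counted, error is about 5.3% to 7.2% under SD-only rules and 5.7% to 8.3% under effect-based rules. These ranges rest on an assumed minimum N of 6 to 10, a maximum of 14 to 34, true SDs of 0.62 and 1.0 mm for the SD-only rules, and a two-sided test. Other rules can fall below 5%, and 14 new subjects would give 5.0%. No early claim is reported from the six, so a further excess from testing twice need not be added. The interim SDs may be in Figures 3c and 3d, which are not available here. Swapping the paired t-test for a 6 + 8 combination test is a trade-off on which statisticians would differ, for a modest and uncertain excess. Keeping the simple test and disclosing the look is defensible.

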## **9. Study period-time table for completion of the project**

Research procedures	5 months	6 months	1 month
Recruitments	X		
Research procedures	X	X	
Data analysis and preparing manuscript			X

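### Does sizing the trial on a six-subject SD mean that 14 subjects fall short of the stated 80% power?

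*Combined protocol and SAP*

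**What the plan says.** Under Approach, item 1 (sample size determination), the plan first gives the original target: 80% power for a 1 mm difference between sides, alpha 0.05 and an SD of 1.0 mm, with mean ridge width as the primary outcome. It then reports a recalculation: "using the interim data from the 6 subjects, 14 subjects will provide 80% power to recognize a significant difference of 0.5 mm". The paragraph names its source (six completed subjects) and the method reference. It gives neither the interim SD nor its confidence limits, and does not say whether the 14 include the six.

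Item 5 (interim data and statistical analysis) fixes the test: "a paired t-test will be performed to compare the changes in the width of alveolar ridge from the two sides". The test's sidedness is not stated. Specific Aim 2 has a no-difference null, "There will be no difference in alveolar bone height and width between the two groups", which points to two-sided. Item 4 (radiographic measurements) sets the endpoint scan: "At 6 months, the follow-up CBCT will be exposed for the maxilla after removal of the mini-screws". Section 9, headed "Study period-time table for completion of the project", marks recruitment only in a first block of 5 months.

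**The concern.** An SD from six pairs carries 5 degrees of freedom. If it is entered into a sample size formula as though known, the resulting power claim depends on a number that could easily be off by half. When the SD is underestimated, the chosen N is too small; because power falls away faster on that side than it rises on the other, average power lies below nominal. If the true SD of the difference were 0.8 or 1.0 mm, a study of 14 would be more likely to miss, or close to missing, a real 0.5 mm effect than the 80% suggests.

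The timetable seems to make matters worse. A subject recruited on the first day of a 5-month recruitment block has no follow-up scan until month 6, so subjects recruited within that block cannot refine the SD while recruitment is open. What would be at stake is whether N should be 18 or 19 rather than 14.

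**Working it through.** **Inputs.** Difference 0.5 mm, N = 14, power 80% (item 1). Alpha 0.05 is stated for the original calculation and assumed to carry over. Paired t-test (item 5). Two-sided is assumed from the null hypothesis. The interim SD is not in the text. Figure 3c-d is not available here; its caption describes mean and SD by side, which is not the SD of the difference.

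**Step 1: the plan's own figure.** It cannot be reproduced forwards without the SD, so solve backwards. Power = P(|T| > t(0.975, n-1)), where T is noncentral t with n-1 df and noncentrality (0.5/SD) × √n. For n = 14 the critical value is 2.160, and 80% power needs noncentrality 3.031. Hence SD = 0.5 × √14 / 3.031 = 0.617 mm. The same calculation gives 0.591 mm for n = 13, 0.563 mm for n = 12 and 0.533 mm for n = 11. If 14 is the smallest sufficient N, the interim SD lay between 0.591 and 0.617 mm. One-sided, the limit at n = 14 is 0.712 mm.

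**Step 2: sensitivity at n = 14, two-sided.**

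| SD of difference (mm) | Power for 0.5 mm |
|---|---|
| 0.617 | 80.0% |
| 0.65 | 75.8% |
| 0.70 | 69.6% |
| 0.80 | 58.1% |
| 1.00 | 41.0% |

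**Step 3: precision of a six-subject SD.** The 95% limits are s × √(5/χ²) at the 97.5% and 2.5% points of chi-square on 5 df, that is 0.624s to 2.453s. For s = 0.617 this is 0.39 to 1.51 mm.

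**Step 4: power averaged over that uncertainty.** Let σ = s × √(5/χ²₅), a standard noninformative choice, and average the power. The answer depends on how the 14 relate to the six.

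| Reading of the 14 | s = 0.617 | s = 0.591 |
|---|---|---|
| 14 subjects, none of them among the six | 70.0% | 72.7% |
| 14 include the six (6 + 8 new) | 73.0% | 75.9% |
| 14 new, pooled with the six (20 in all) | 83.7% | 85.8% |

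The second and third rows were simulated, holding the six subjects' SD at s. If 14 already holds a margin of two subjects (s from 0.533 to 0.563 mm), the first row becomes 76-79% and the second 79-82%.

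**Step 5: where 18 or 19 comes from.** On the first reading only, 80% average power needs 18 subjects at s = 0.591 (80.7%) or 19 at s = 0.617 (80.0%). On the third reading the average already exceeds 80%.

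**Step 6: the original target.** For 1 mm with an SD of 1.0 mm, read as the SD of the difference, 10 pairs give 80.3% power and 14 give 93.2%.

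**The case for a change.** The strongest case for acting is that the arithmetic is sound and does not hang on the prior. Fix the true SD, draw six-subject SDs repeatedly, and size each time for a nominal 80%: average actual power comes out at 71-77% for true SDs of 0.5 to 1.0 mm. Using a one-sided test hardly alters the first reading, at 71-74%. Half the interim subjects had their screws removed at 8 months, not 6, so the interim SD may not describe a 6-month endpoint. Printing the SD with a sensitivity table would cost only wording.

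Much of this stands. A six-subject SD is imprecise, and the 80% should be read as conditional on it. What does not stand is the step to a shortfall in this trial. The repeated-sampling check also assumes that the final subjects are separate from the six. The SD is inferred from the 14 and may be wrong if N was rounded up or a cautious SD was used. The timetable argument holds only for subjects recruited within that table; the study is described as ongoing, and the documents do not say whether others are already in follow-up. Nor does the plan promise a second recalculation.

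**Conclusion.** The concern is right about imprecision but does not establish an error. Given a two-sided 0.05 paired t-test, 80% power for 0.5 mm at N = 14 requires an SD of the difference no larger than 0.617 mm. Average power could be as low as 70% or as high as 86%, depending on whether the 14 exclude, include or are added to the six, and on an SD between 0.591 and 0.617 mm.

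None of the possible remedies is compelled:

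- **Printing the SD and a sensitivity table** fills in reporting detail. A statistician can recover the 0.617 mm limit from the stated N, power and difference, as shown above. The planning SD plays no part in the final paired t-test, which uses the SD observed in the data.
- **Raising N to 18 or 19** would give four or five more people a mini-screw and a follow-up scan ("Limited volume CBCT with high resolution will be exposed; this is a study procedure") to cure a shortfall that appears on some readings and not on others.
- **Replacing conditional power with power averaged over a prior** is a legitimate preference, but experienced statisticians differ on it, and the conventional statement is not wrong for being conditional.

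The plan says openly that its recalculation rests on six subjects, so a reader can judge how far to trust the 80%.
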